### 2.1 Sample size calculation

The unit of analysis for this study is ED patients with suspected sepsis. The necessary enrollment size was used to calculate the study period necessary to achieve power, based on historic volume trends. The main calculations were done using the `pwr` package for R.

During the study period, we expect 2054 patients to be identified and exposed to decision support (CDS). With current care patterns, we would expect 25% (514) to receive guideline-

concordant septic shock care prior to shock occurring. In the literature, use of pediatric sepsis quality interventions has increased rates of concordant early care of shock to 50% (1027). With an estimated effect of the alert of increasing rates of concordant care from 25% to 50%, using a significance of 0.05, we anticipate >90% power to detect this difference. We will have 80% power to detect an increase of 6%.

For the outcome of time to receipt of antibiotic, we expect that 79% of patients will receive antibiotics. Among those who do receive antibiotics, with current care patterns, in pilot data we have observed a mean time to antibiotics of 55 minutes, or a mean log time of 4.0 (SD 1.29). In published pediatric sepsis literature, the use of pediatric sepsis quality interventions has decreased the log time to antibiotic to 3.3 (SD 1.54). Using a significance of 0.05, we anticipate >90% power to detect a difference in this outcome. We have 80% power to detect a smaller difference of 4.0 vs 3.8 (55 to 45 minutes). Even under conditions of very slow accrual where half of the hypothesised sample is realized, we would have 80% power to detect a difference of 4.0 vs 3.72 (55 to 41 minutes).

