#### 4.2 Secondary outcomes

##### Time to Antibiotics

Time to antibiotics will be measured in minutes from the time of sepsis recognition to the start of intravenous antibiotic treatment. This will be a time-to-event outcome. Sepsis recognition is defined as the earlier of: sepsis page sent, sepsis orderset use, or intravenous antibiotic order.

[Time Frame: Up to 24 hours after Emergency Department arrival]

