##### Number of Patients Receiving Intravenous Antibiotics during Emergency Department care

[Time Frame: Up to 24 hours after Emergency Department arrival]

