##### Other hospital course and resource utilization outcomes

Organ dysfunction laboratories measured

Sepsis orderset used

Arrival to Antibiotic Administration

ED Disposition

24-Hour hypotension

Intravenous crystalloid fluid volume administered/kg in the first 24 hours

Vasoactive agent used during hospitalization

Positive pressure ventilation during hospitalization

Hospital Length of Stay

ICU within 24 hours

ICU Length of Stay

Proportion of all ED patients triggering the CDS

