### 6.2 Secondary outcomes (continuous – time to antibiotic)

The secondary hypothesis will test whether the time to antibiotics is shorter in the intervention arm compared to the control arm. A hazard ratio will be calculated to assess this, and considered significant if the 95% confidence interval does not contain 1.0. The following approach will be used.

Time will be measured beginning with admission to the ED and concluding with administration of antibiotics (an event) or discharge from the ED (censoring). Death is expected to be rare and will be treated as a censoring event. Analysis will use a Cox proportional hazard model with a fixed binary effect for treatment.

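### Time to antibiotics is defined from sepsis recognition in Section 4.2, but the Cox model in Section 6.2 that tests it starts the clock at ED admission.

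*SAP*

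**What the plan says.** Section 4.2, under Time to Antibiotics, gives the definition: "Time to antibiotics will be measured in minutes from the time of sepsis recognition to the start of intravenous antibiotic treatment". It calls this a time-to-event outcome and fixes the origin: "Sepsis recognition is defined as the earlier of: sepsis page sent, sepsis orderset use, or intravenous antibiotic order". The time frame is up to 24 hours after ED arrival.

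Section 6.2 states the secondary hypothesis that time to antibiotics is shorter with the intervention. It announces "The following approach will be used" and then sets the clock: "Time will be measured beginning with admission to the ED and concluding with administration of antibiotics (an event) or discharge from the ED (censoring"). The model is a Cox regression with one binary treatment effect. The result counts as significant if the 95% confidence interval for the hazard ratio excludes 1.0.

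The list of other hospital course and resource utilization outcomes in Section 4.2 carries a separate item, "Arrival to Antibiotic Administration".

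Section 2.1 gives the planning figures, "we expect that 79% of patients will receive antibiotics" and "in pilot data we have observed a mean time to antibiotics of 55 minutes". It does not say from which origin the 55 minutes were measured.

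**The concern.** One named outcome has two time origins. The difference between them is the interval from arrival to recognition, and that is where an early-prediction tool may act.

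- The arrival clock credits the tool with earlier recognition. The recognition clock does not.
- If the tool speeds only the step from recognition to antibiotic, the arrival clock dilutes that effect.

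The two hazard ratios can therefore differ, and either can be the larger. A result reported as the secondary outcome of Section 4.2 would in fact be the lower-tier arrival-to-antibiotic outcome. With both texts in force, the clock could also be chosen after the data are seen.

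**Working it through.** **1. The text side by side**

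| Place in SAP | Start | End |
|---|---|---|
| 4.2, Time to Antibiotics | sepsis recognition | start of IV antibiotic |
| 4.2, other outcomes | arrival | antibiotic administration |
| 6.2, Cox model for the secondary hypothesis | ED admission | antibiotic administration, or censoring at ED discharge |

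The third row matches the second, not the first. Section 6 otherwise offers only a general linear-model framework, with an odds ratio for the primary outcome. No section analyses the recognition-based time.

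**2. Do the planning figures settle the origin?**

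They do not. The stated power reproduces with a two-sided 5% comparison of mean log times, power = Φ(δ / (σ√(2/n)) − 1.96).

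- σ = √((1.29² + 1.54²)/2) = 1.42.
- Full sample: n = 0.79 × 2,054 / 2 = 811 per arm. For 4.0 vs 3.8, δ = 0.2 and power = 0.809.
- Half sample: n = 406 per arm. For 4.0 vs 3.72, δ = 0.28 and power = 0.802.
- For 4.0 vs 3.3, power exceeds 0.999.

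Equal arms follow if site-periods are of equal size, since 10 of the 20 are intervention periods. None of these figures names a clock.

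**3. How far apart can the clocks be? (illustration)**

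The SAP gives no arrival-to-recognition data, so these inputs are assumed: lognormal, median 30, 60 or 120 minutes, log SD 0.8. From Section 2.1: log mean 4.0 and SD 1.29, here used for recognition to antibiotic, and 79% treated. Untreated children stay at risk to 24 hours after arrival on both clocks, so only the origin differs. A Cox model with one binary effect was fitted to simulated cohorts of 1 to 2 million children.

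| What the tool changes | Arrival-clock HR (30 / 60 / 120 min) | Recognition-clock HR |
|---|---|---|
| Halves arrival to recognition only | 1.10 / 1.16 / 1.24 | 1.00 |
| Cuts it by 18% only | 1.04 / 1.05 / 1.07 | 1.00 |
| Recognition to antibiotic only, log 4.0 to 3.3, SD 1.29 in both arms | 1.21 / 1.18 / 1.14 | 1.25 |
| Same, with Section 2.1's SD of 1.54 in the intervention arm | 1.16 / 1.13 / 1.10 | 1.20 |

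The halving and the 18% cut borrow the relative sizes of 4.0 to 3.3 and 4.0 to 3.8. They are not recognition data.

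Sensitivity of the halving case:

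- At 60 minutes, a log SD of 0.5 or 1.0 gives 1.17 or 1.15 on the arrival clock.
- If the 55 minutes is already arrival-based and 20%, 40% or 60% of it precedes recognition, halving that part gives about 1.04, 1.08 or 1.12 against 1.00.
- With censoring at ED discharge as Section 6.2 has it (ED stay assumed lognormal, median 240 minutes, log SD 0.5), the arrival clock gives 1.16, 1.31 and 1.58 against 1.00.

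**4. Can this change the declared result?**

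Expected events are 0.79 × 2,054 = 1,623. With equal arms and independent patients, SE(log HR) ≈ 2/√1,623 = 0.050. An HR of 1.16 gives z = ln(1.16)/0.050 ≈ 3.0, and an HR of 1.00 gives z = 0. In that scenario the clock alone decides whether the confidence interval excludes 1.0. Clustering by site would lower z.

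**5. Children with no recognition time**

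A child given IV antibiotics has an order and so a time zero. If the 79% refers to IV antibiotics, those without a time zero number at most 0.21 × 2,054 = 431. The possible range is 0 to 431, because the inclusion criteria are not shown. Dropping 108 of 1,027 in each arm leaves the HR at 1.00. Dropping 108 controls but 54 intervention children gives 0.88 with no true effect. That split is hypothetical.

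**The case against.** The strongest reply is that Section 6.2 leaves nothing open. It fixes the event, censoring, model, effect measure and decision rule, and only the origin clashes with Section 4.2. That is right as far as it goes. A programmer could run Section 6.2 today, but the output would not be the outcome that Section 4.2 defines.

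A second reply is that this is one secondary outcome and that the hazard ratios rest on the reviewer's inputs. Both points are fair. The simulated figures are no evidence about this trial, and the main table uses 24-hour follow-up rather than the ED-discharge censoring of Section 6.2. The contradiction needs none of them. Under the assumed ED stay, Section 6.2's censoring widens the gap in the halving case.

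A third is that children without a time zero may not exist, if entry itself requires a page, orderset or antibiotic order. That is possible and is why the range starts at 0. A handling rule is still needed on the recognition clock unless entry guarantees a recognition time.

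Finally, the 24-hour frame in Section 4.2 need not conflict with censoring at ED discharge. The same frame is attached to "Number of Patients Receiving Intravenous Antibiotics during Emergency Department care", so it may be only an outer window.

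**Conclusion.** The concern holds and should be fixed before analysis. Sections 4.2 and 6.2 give different origins for the same secondary outcome, and the SAP itself lists the arrival-based interval as a separate quantity. This rests on the text alone.

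The size cannot be known from the SAP. Under the stated assumptions the arrival clock shows a hazard ratio of 1.04 to 1.24 where the recognition clock shows 1.00. When the tool acts only after recognition, the arrival clock instead understates the effect: 1.10 to 1.16 against 1.20 with Section 2.1's own SDs. The primary outcome and the arithmetic of the stated power are unaffected.

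**What to change.** Use one time origin in Sections 4.2 and 6.2.

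- **Option (a), preferred.** Change Section 6.2 to start at sepsis recognition. Report the arrival-clock Cox model under the separately listed arrival-to-antibiotic outcome. State how children with no page, orderset use or IV antibiotic order are handled, and report their number by arm. The cost is at most one extra Cox model and one rule. This keeps the declared outcome and the anchor it shares with the primary outcome.
- **Option (b).** Change Section 4.2 to the arrival clock, which gives every child a time zero, and delete the duplicate item. The edit is short, but it redefines a declared secondary outcome and must be documented as such.

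Under either option, state in Section 2.1 which clock the 55-minute pilot figure uses. As a minor addition, one sentence should say whether follow-up ends at ED discharge or at 24 hours.

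### The two 80% power figures for time to antibiotics belong to a comparison of log times in recipients, not to the Cox model planned in SAP section 6.2

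*SAP*

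**What the plan says.** SAP section 2.1 sizes this outcome on the log-minute scale, among recipients only.

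- Recipients: "we expect that 79% of patients will receive antibiotics".
- Control arm, from pilot data: "mean time to antibiotics of 55 minutes, or a mean log time of 4.0 (SD 1.29").
- Intervention arm, from published quality interventions: "decreased the log time to antibiotic to 3.3 (SD 1.54"). For this target the section says "Using a significance of 0.05, we anticipate >90% power to detect a difference in this outcome".
- Two smaller effects follow. At full sample: "We have 80% power to detect a smaller difference of 4.0 vs 3.8 (55 to 45 minutes"). At half the sample: "we would have 80% power to detect a difference of 4.0 vs 3.72 (55 to 41 minutes").

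No SD is attached to 3.8 or 3.72. The section does not name the test. It does name the `pwr` package, and for this outcome it cites a primer on effect sizes for t-tests and ANOVAs.

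Section 6.2 plans another analysis: "Analysis will use a Cox proportional hazard model with a fixed binary effect for treatment". The result is a hazard ratio. The event is antibiotic administration, and leaving the ED without it is censoring. Section 5.1 puts all patients who meet the inclusion criteria in the main analysis. The SAP gives no target hazard ratio, no power for this model, no check of proportional hazards and no fallback.

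**The concern.** A difference in mean log time among recipients and a hazard ratio over all patients are different estimands with different tests. Power for one does not carry over to the other. Two features could separate them here.

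1. About 21% of patients never receive an antibiotic. They are absent from the sizing but sit in the Cox risk set until they leave the ED.
2. If log times are more spread out in the intervention arm, the hazard ratio changes over time and can cross 1, so a single ratio averages opposing effects.

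At stake is whether the SAP may tell its readers that differences of 0.20 and 0.28 log minutes are detectable with 80% power, the second even with half the sample.

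**Working it through.** **Inputs.** Section 2.1: 2054 patients, 79% recipients, log means 4.0, 3.8, 3.72 and 3.3, SDs 1.29 and 1.54, significance 0.05. Section 6 makes tests two-sided. Section 2 has 4 sites × 5 periods = 20 site-periods, of which 4 + 3 + 2 + 1 = 10 are on intervention. With equal volumes that is 1:1.

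**Step 1: reproduce the stated 80%.** Recipients: 2054 × 0.79 = 1623, or 811 per arm. Pooled SD = √((1.29² + 1.54²)/2) = 1.42. Power = Φ(δ / (SD·√(2/n)) − 1.96).

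- Full sample, δ = 0.20: 0.20 / (1.42 × √(2/811)) = 2.83, and Φ(0.87) = 81%.
- Half sample, δ = 0.28, n about 406: 0.28 / (1.42 × √(2/406)) = 2.81, and Φ(0.85) = 80%.

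Other readings of the full-sample figure do not fit: SD 1.29 gives 88%, SD 1.54 gives 74%, and all 2054 patients with SD 1.42 give 89%. So the 80% rests on recipients only, with an SD of about 1.42.

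**Step 2: power of the planned Cox model.** I simulated 1:1 allocation, 79% recipients in both arms and no clustering. The SAP gives no ED stays, so I assumed log-normal stays with medians from 120 to 480 min and a log-SD of 0.5. Section 6.2 can be read two ways. Either only non-recipients are censored at discharge, or discharge also cuts off recipients whose antibiotic would come later. Each setting had 800 to 4000 simulated trials.

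| Recipients' times | Full sample, 4.0 vs 3.8 | Half sample, 4.0 vs 3.72 |
|---|---|---|
| Log-normal, SDs 1.29 / 1.54, only non-recipients censored | 5–8% | 10–12% |
| Log-normal, SDs 1.29 / 1.54, discharge censors all | 9–28% | 16–33% |
| Log-normal, common SD (1.29, 1.42 or 1.54), both readings | 27–58% | 24–55% |
| Weibull, common SD (same values), both readings | 29–81% | 28–79% |

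If non-recipients stay at risk until after the last event, log-normal power with common SD 1.42 is 21% at either sample size. On the same simulated log-normal data with SDs of 1.29 and 1.54 or a common 1.42, the t-test on log time in recipients had about 80–82%.

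The top of the Weibull row is the edge of the range: SD 1.29, median stay 120 min, only non-recipients censored. Shorter or more uniform stays push it higher. At a median of 60 min, full-sample power is about 90–96% (SD 1.42 and 1.29). With a log-SD of stay of 0.3, it is 85–89% at 120 min and about 80% at 150 min.

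**Step 3: the two causes.**

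*Non-recipients in the risk set.* With Weibull times and a common SD, hazards in recipients are exactly proportional, with log hazard ratio πδ/(√6·SD). For δ = 0.20 and SD 1.42 that is 0.181. With 1623 events, 0.181 × √1623 / 2 = 3.64, and Φ(3.64 − 1.96) = 95%. SD 1.29 gives 98%. The fall to the all-patient figures therefore comes only from the non-recipients. The reason is simple: if both arms end with 79% treated and everyone else still at risk, the cumulative hazard ends at −ln(0.21) = 1.56 in each. A ratio above 1 early must be offset by one below 1 later.

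*Crossing hazards, if the intervention SD is 1.54.* Under log-normal times, 3.8/1.54 vs 4.0/1.29 gives hazard ratios of 1.78 at 5 min, 1.00 at about 33 min, 0.92 at 60 min and 0.81 at 240 min. At 33 min about 65% of control recipients are still untreated. Cox power in recipients alone is then about 8%. With a common SD of 1.42 the ratio falls from 1.28 at 5 min to 1.05 at 24 h without crossing, and power in recipients is about 72%.

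**Step 4: the main target.** For 4.0 vs 3.3 the planned Cox model keeps 95–100% power in every setting tried.

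**The case against.** The strongest reply concerns the cause. A reader might infer that the SAP's own figures imply strongly non-proportional hazards and that this alone removes the power. The document does not support that. SD 1.54 is attached only to the published value of 3.3, while 1.29 comes from local pilot data, so the gap may reflect the sources rather than the treatment. Nor does the SAP say that times are log-normal. An exponential time has a log-SD of π/√6 = 1.283, almost exactly the control value. With a common SD the hazards need not cross. This stands, and it is why the result is given as a range with two causes.

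A reader might also infer that a true shift from 55 to 45 minutes would yield a hazard ratio near 1 and be reported as no effect. That needs the spread to widen as well. In that case the log-normal arithmetic mean rises from exp(4.0 + 1.29²/2) = 125 to exp(3.8 + 1.54²/2) = 146 minutes, so a near-null ratio reflects a mixed effect rather than a missed benefit. A pure shift keeps the ratio above 1 in recipients.

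Three further replies have some force. The t-test is inferred, not named. Receipt was held at 79% in both arms, and a rise under the intervention would increase Cox power. The outcome is secondary, and no sample size rests on the two figures. None of this makes the 80% a property of the planned model.

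**Conclusion.** The point holds in a limited form. The two 80% statements in section 2.1 describe a comparison of log time in recipients. For the Cox model in section 6.2, all-patient power at those effects is roughly 5–35% if the SDs are 1.29 and 1.54, 20–60% with a common SD and log-normal times, and 30–80% with a common SD and Weibull times.

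That the 80% was not computed for the planned model is certain. The size of the shortfall is not. It rests on assumed ED stays (median 120 min or longer), the shape of the time distribution, the SD at 3.8 and 3.72, equal receipt in both arms, and no clustering. Under Weibull times with short or uniform stays for non-recipients there may be no shortfall.

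It would be wrong to conclude that the outcome is underpowered for its main target: the power above 90% for 4.0 vs 3.3 survives. The different clock starts in sections 4.2 and 6.2 are a separate matter, as is clustering by site and period, which both calculations ignore.

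**What to change.** In section 2.1, replace the two 80% figures with power computed for the Cox model in 6.2, stating the SDs, the time distribution, the share of non-recipients and the assumed ED stay. Alternatively, keep the figures and label them as power for a comparison of log time in recipients.

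In section 6.2, add a check of proportional hazards. Pre-specify one supporting analysis that does not rely on them and matches the sizing, such as a log-normal accelerated failure time model or a comparison of log time in recipients. Report it beside the proportion treated in each arm, because an analysis of recipients alone says nothing about who was treated.

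The cost is SAP wording and one simulation. No more patients or data are needed. If the figures are recomputed, the stated power for the smaller effects will probably be less favourable.

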## 7. Missing data

Missing data are not expected in this dataset, which only includes existing clinical data on patients through hospital discharge or 30 days, whichever happens first.

